## 14 DATA MANAGEMENT

On umbrella study level information about eligibility, demographics, medical, hearing and device history, protocol deviations and completion of study will be obtained. On sub-study level also adverse event, device deficiency and sub-study specific information will be captured.

The CRF will capture the datapoints necessary to determine the subject status according to the criteria described in section 7.2.5.

Source data will be captured in clinic notes, paper-based source data worksheets, questionnaires or printed directly from testing software. Data such as clinical performance data, questionnaires etc. can be entered directly into the eCRF which shall be considered source data for these items. If electronic medical records do not permit read only access for monitoring purposes, a certified printout must be provided.

The system used for data collection will be specified at the sub-study level, including the use of electronic data capture (EDC) on eCRFs.

In addition, de-identified electronically generated data will be collected from clinical fitting software, objectives measures software, imaging (such as CT), videography, diagnostic tools etc. The unamended data file shall be regarded as the source.

In case the full eCRF option is not utilized, data collection for demographics, device exposure, medical history, adverse events, device deficiencies, concomitant medications, protocol deviations and completion will be performed using electronic data capture (EDC) on electronic Case Report Forms (Safety eCRF), to support safety analysis and reporting. All other data will be collected from clinical fitting software, objectives measures software, imaging, videography, clinical performance data etc. or captured into paper Case Report Forms and entered in a suitable database or directly into the study report after review by the study monitor. In case specific procedures are used for data management such as data collection and review, this will be specified in the sub-study documentation. Site personnel will be trained on the completion of the CRFs. Unamended data files shall be regarded as the source.

Site personnel will be trained on the completion of the eCRF prior to obtaining access to the system and will have their own Login/Password. Access to clinical study information will be based on an individual's role and responsibilities.

The eCRF will have role-based user permissions for data entry, viewing, and reporting options. All communications between users and the EDC server are encrypted. Web servers are protected by a managed firewall. This application is designed to be in compliance with applicable regulations including 21 CFR Part 11.

The application will include programmed data consistency checks and supports manual generation of data clarifications/queries, including documentation of site responses. The application maintains a comprehensive audit trail for all data entered, including updates and queries, and documents the time that each entry occurred and who made the entry.

Principal Investigators will affirm that the data for each subject at their site is accurate and complete by way of an electronic signature.

## **15 CONFIDENTIALITY**

The investigator and site staff will collect and process personal data of the subjects in accordance with governing data privacy regulations [such as the EU GDPR regulations].

Data will be reported to the Sponsor on CRFs or related documents (e.g. questionnaires). Subjects will be identified on CRFs and other related documents only by a unique subject identification code and shall not include the subject's name or other personal identifiable information. Completed CRFs or related documents are confidential and will only be available to the Investigator and site staff, the Sponsor and their representatives, and if requested to the Ethics Committee and national regulatory authorities. Publications or submission to a regulatory authority shall not disclose the identity of any subject.

## **16 ETHICS COMMITTEE AND REGULATORY AUTHORITY APPROVAL**

The clinical investigation will not commence prior to the written favourable opinion or approval from the EC and or regulatory authority (if appropriate) is obtained.

The final Sponsor-approved version of the CIP, Informed Consent Form, and other necessary documents shall be submitted to the EC. A copy of the EC opinion/approval shall be provided to the Sponsor.

Clinical Investigation Plan |

Approval Date (GMT+

The Investigator shall forward to the Sponsor, for review and approval, any amendment made to the approved ICF and any other written information to be provided to the subject prior to submission to the EC.

The Sponsor and Principal Investigator will continue communications with the EC, as required by national regulations, the clinical investigational plan, or the responsible regulatory authority.

Any additional requirements imposed by the EC or regulatory authority will be implemented by the Sponsor.

The Investigator shall submit the appropriate documentation if any extension or renewal of the EC approval is required. In particular, substantial amendments to the CIP, the ICF, or other written information provided to subjects will be approved in writing by the EC.

The Investigator shall report to the EC any new information that may affect the safety of the subjects or the conduct of the clinical investigation. The Investigator will send written status summaries of the investigation to the EC regularly, as per local EC requirements.

Upon completion of the clinical investigation, the Investigator shall provide the EC with a brief report of the outcome of the clinical investigation, as per local EC requirements.

The clinical investigation is covered by clinical trial insurance, meeting the requirements of the participating countries.

## **17 SUSPENSION OR PREMATURE TERMINATION**

The Sponsor will discontinue the clinical investigation site if:

- 1) major non-adherence to the CIP or GCP principles is occurring
- 2) it is anticipated that the subject recruitment will not be adequate to meet the objectives of the clinical investigation

An ongoing clinical investigation may be discontinued in case of:

- 1) device failure
- 2) serious or intolerable ADE, leading to the explant or discontinued use of the device
- 3) subject's death

In case of a blind sub-study, the criteria for access to and breaking the blinding/masking code in the case of suspension or premature termination of the clinical investigation will be described in the sub-study documentation.

CTC: Upon end of a clinical investigation, the sponsor shall notify the regulatory authority within 15 days. In the case the clinical investigation is temporarily halted or terminated early, notification of this shall be made to the regulatory authority within 15 days. Justification for the halt or termination shall be included. If either situation is on safety grounds, then the reporting timeframe is 24 hours.

Cochlear Melbourne: If a trial is prematurely terminated or suspended, the sponsor should promptly inform the investigator(s), institution(s), the ethics committee, and the TGA. The sponsor should provide the reason(s) for the termination or suspension.

## **18 AMENDMENTS TO THE CLINICAL INVESTIGATION PLAN**

Clinical Investigation Plan | Approval Date (GMT+

No changes in the CIP or investigation procedures shall be made without mutual agreement of the Principal Investigators and the Sponsor. This agreement will be documented as a CIP amendment. Amendments will require notification to the Ethics Committees (ECs) by the Principal Investigators (and to the relevant regulatory authority(s) by the Sponsor, if applicable).

## **19 RECORD KEEPING AND RETENTION**

Data generated from the clinical investigation will be stored in a limited-access file area and be accessible only to representatives of the study site, the Sponsor and its representatives, and relevant health authorities/regulatory agencies. All reports and communications relating to study subjects will identify subjects only by subject unique identification code. Complete subject identification will be maintained by the Investigator. This information will be treated with strict adherence to professional standards of confidentiality.

The investigator must retain study-related records for a period of at least 15 years after completion of the investigation or after the last device was placed on the market, if the IMD has market authorisation.

The Sponsor will notify the Principal Investigator when records are no longer needed. The Investigator will not discard any records without notifying the Sponsor. If the Principal Investigator moves from the current investigational site, the Sponsor should be notified of the name of the person who will assume responsibility for maintenance of the records at the investigational site or the new address at which the records will be stored. The Investigator will notify the Sponsor as soon as possible in the event of accidental loss or destruction of any study documentation.

## **20 PUBLICATION POLICY**

This clinical investigation will be retrospectively registered at a public clinical trial registry ClinicalTrials.gov. Due to the local Ethics Committee requirement, the results from sub-studies with participation from Melbourne sites will be reported in the public clinical trial registry.

A joint peer-reviewed publication authored by the clinical investigator(s) and Sponsor may be prepared. In addition, the results of the clinical investigation may also be disseminated as conference presentations (for example abstract and poster session). Manuscript authorship and responsibilities will be discussed and agreed upon prior to investigation start and in accordance with guidelines and recommendations provided by the International Committee of Medical Journal Editors (ICMJE) to enable communication in a timely manner. All contributors who do not meet the criteria for authorship will be listed in an acknowledgments section of the publication.

Further details are described in the Clinical Investigation Research Agreement (CIRA) of the study.

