The umbrella investigation will be conducted in different sub-studies to assess the incremental change of the software functionality and/or to assess the concept of a new diagnostic, fitting or (re)habilitation method. Each sub-study will be submitted separately with a sub-study specific Clinical Investigation Plan (CIP) and a sub-study specific Informed Consent Form (ICF). A status update will be reported yearly, and a close-out report will be provided at the end of the study. For each sub-study a Clinical Investigation Report (CIR) will be delivered. Since different methods will be tested, subjects may be recruited for multiple sub-studies or stages of the project. Each subject can only participate in one sub-study at a time. This is further described in section 7.

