#### 7.1.1 Design Rationale

The goals of this study are

- to measure hearing outcomes to assess performance and/or
- to obtain better diagnostics and/or
- to achieve higher convenience for implant users and hearing care professionals and/or

• to determine whether device and procedure improvements deliver an improvement in time efficiency for the CI recipient and the clinician involved in the CI process.

The outcomes of the study will guide Cochlear to select features for inclusion in future cochlear implant systems and/or future models of care.

This investigation can be divided in two stages, namely the intra-operative stage and the post-operative stage, during which evaluation will take place.

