#### 7.2.4 Vulnerable Populations

As described in previous sections, this umbrella study will evaluate the benefit of new features. Each method/tool will be evaluated in a sub-study. Depending on the specific aspect that will be tested, children might be involved from the age of 10 months upwards. The sub-study specific information will be given to the parents/ legally designated representative of the subject and will be adapted as well towards the cognitive level of the subject. The Informed Consent Form (ICF) will be signed by the parents and/or legally designated representative of the subject.

Paediatric subjects will be enrolled in Belgium only.

No extra medical care will need to be provided after the clinical investigation.

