## **9 STATISTICAL CONSIDERATIONS**

### 9.1 General Considerations

Data will be analysed separately per sub-study. Analysis of the data will take place at Cochlear. Substudy specific endpoints and other statistical considerations such as hypothesis and sample size

determination will be described in the sub-study documentation and a sub-study CIR will be written when these endpoints are reached.

Clinical Investigation Plan |

Approval Date (GMT+

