## **25 CHANGE HISTORY**

Version	Change	Rationale
1.0	Introduction CIP	NA
2.0	Section 17: "Upon end of a clinical investigation, the sponsor shall notify the regulatory authority within 15 days. In the case the clinical investigation is temporarily halted or terminated early, notification of this shall be made to the regulatory authority within 15 days. Justification for the halt or termination shall be included. If either situation is on safety grounds, then the reporting timeframe is 24 hours."	Specified the process of reporting end of a clinical investigation to the regulatory authority.
3.0	Section 11.4.2: "The sponsor is responsible for reporting serious adverse events (SAE) to Famhp (Federal Agency for Medicines and Health Products): [contact], by using the European form. Reporting must be a) immediately for any SAE or device deficiency (DD) that might have led to a SAE resulting in death or threat to life, or is associated with imminent risk of death, or for any serious injury or disease warranting rapid curative therapy or any new information relating thereto, and b) immediately and in any case no later than 7 days for other SAE/SADEs. In case an initial notification of an SAE/SADE would be incomplete, on receipt of additional information the Sponsor must submit a clearly referenced and numbered follow-up report of the event."	Specified the process of reporting adverse events to the regulatory authority.
4.0	Updated sponsor details on pages 1 and 2; added CRO details in page 2; updated number of subjects, number of sits and inclusion criteria in synopsis; updated section 5.1 (deleted information on risk management and device control, has been mentioned in	Cochlear Melbourne (internal site) and HEARnet, Melbourne (external site) have been added as additional sites under the current umbrella study. Details regarding the updated subject numbers, sites and associated reporting requirements to competent authority and ethics have been added. Inclusion criteria has been modified to

**Cochlear**®

| 6.0

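### Should Section 20 commit to public results for every sub-study, and not only for those with Melbourne participation?

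*Combined protocol and SAP*

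**What the plan says.** Section 20 does three separate things. It registers the whole investigation, retrospectively, on ClinicalTrials.gov. It promises, because a local ethics committee requires it, that "the results from sub-studies with participation from Melbourne sites will be reported in the public clinical trial registry". And it leaves everything else open: "A joint peer-reviewed publication authored by the clinical investigator(s) and Sponsor may be prepared", conference presentation is likewise optional, and further terms are left to the research agreement.

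Two other parts of the protocol determine who falls outside that promise. Section 7.2.4 states "Paediatric subjects will be enrolled in Belgium only", and the Synopsis restricts Australia to adults. Section 25 records for version 4.0 that "Cochlear Melbourne (internal site) and HEARnet, Melbourne (external site) have been added as additional sites under the current umbrella study".

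On non-public reporting, Section 4.1 states "For each sub-study a Clinical Investigation Report (CIR) will be delivered" and adds a yearly status update and a close-out report. Section 16 requires a brief outcome report to the ethics committee. Section 9.1 words the timing of the sub-study report as "a sub-study CIR will be written when these endpoints are reached". On use of the results, Section 7.1.1 says "The outcomes of the study will guide Cochlear to select features for inclusion in future cochlear implant systems and/or future models of care".

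**The concern.** The umbrella has no primary hypothesis of its own (Section 9.3.1) and data are analysed sub-study by sub-study (Section 9.1). Its evidence is therefore the set of sub-study results. If only part of that set must be made public, and the part is picked by site and not by question, the public record may not represent the whole.

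Two groups appear to drop out by construction: any purely paediatric sub-study, and any sub-study that finished before the Melbourne sites joined. The paediatric group matters most, because Section 7.1.1 says children need methods adapted to them, so adult results cannot stand in.

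Two smaller worries sit alongside. Section 9.1 ties the report to endpoints being reached, while Section 17 begins a list with "An ongoing clinical investigation may be discontinued in case of", so a sub-study that stops early might seem to owe no report. And the word score became the umbrella primary endpoint in version 6.0, without a statement of how it relates to the endpoint of a fitting sub-study already under way.

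**Working it through.** The plan gives no figure to reproduce, so the check sets the sections side by side.

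**1. Which sub-studies lack a stated commitment?** Section 20 covers a sub-study if a Melbourne site takes part.
- Belgian and Melbourne sites together: covered, including a mixed sub-study with Belgian children and Melbourne adults.
- Belgian sites only: no commitment stated.
- Purely paediatric: no commitment stated, since Australia enrols no children. Section 7.2.3 makes paediatric recruitment conditional on a sub-study strictly needing it, so this group may be empty.
- Completed before version 4.0: no commitment stated. No such sub-study is identified in the documents.

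**2. Does another section make those results public?** No. The sub-study reports, yearly updates, close-out report and ethics committee report are not described as public. Section 21 binds the study to applicable regional and national regulations, and Section 20 points to the research agreement; neither the content of those rules nor the agreement is in the documents. The supportable statement is that this plan sets out no such commitment, not that none exists.

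**3. Does posting touch any result?** Follow a sub-study through the plan. Its endpoints come from the sub-study documentation (Section 9.2), its primary analysis is done at sub-study level (Section 9.6), and its report is promised without condition (Section 4.1). No step refers to the registry. Posted or not, the data, the estimate and the conclusion are the same.

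**4. Does partial posting bias feature selection?** That decision is the sponsor's (Section 7.1.1). The sponsor analyses the data (Section 9.1) and a report is delivered for every sub-study, so its decision does not rest on the posted subset.

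**5. How large is the gap?**
- Sites: 5 planned (Synopsis) − 2 Australian (Section 7.3) = 3, and 3/5 = 60%. This is a share of sites, not of sub-studies. A sub-study run at all 5 sites is fully covered.
- Protocol versions without Melbourne: 1.0, 2.0 and 3.0, or 3 of 6. This counts document revisions, not time, subjects or sub-studies.
- Share of sub-studies without a commitment: not computable, because neither the number of sub-studies nor the country split of the 160 subjects is given.

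**6. The two smaller worries.** Section 4.1 promises a report for every sub-study. Section 9.1 reads naturally as saying when it is written, and nothing in Section 17 waives it, so the two differ in wording only. On the endpoint, Sections 9.2 and 9.6 leave detail to the sub-study documentation. The version 6.0 rationale in Section 25 wants one consistent measure in all fitting sub-studies, so a sentence exempting those already started would settle a question the plan leaves open, and would sit awkwardly with that aim.

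**The case for a change.** The strongest case for a change is that outside checks on this programme are few. Sponsor staff may run study procedures, and Section 7.6 concedes that potential bias is not mitigated, offering only blinding where possible. Analysis is in-house (Section 9.1) and there is no data monitoring committee (Section 11.5). Public results would be one of the few remaining checks. Section 20 gives no scientific reason for dividing results by site. The registry entry will exist anyway, so posting the remaining sub-studies would add only modest work, and Section 15 already protects identities in publications.

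Much of this stands. Someone outside the sponsor who wants to learn from the programme could be left with a partial record, and a commitment covering every sub-study would be good practice.

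Two things limit it. First, none of it shows a result, analysis or decision within the investigation that would come out differently; posting makes results visible but does not remove the sources of bias named. Second, the cost is more than a sentence. A protocol change needs agreement between the principal investigators and the sponsor plus ethics committee notification (Section 18), and written approval if it is substantial (Section 16). Pre-market feasibility results would become public. Reaching back to sub-studies completed before version 4.0 would also apply new terms to work done under consent forms and agreements that are not visible here.

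**Conclusion.** The reading of Section 20 is right: this plan states no public-results commitment for a Belgian-only sub-study. No change is called for. The clause sets a disclosure minimum, gives its reason, and does not bar wider posting. Applying it as written leaves every sub-study's data, analysis, report and conclusion untouched. The choice between that minimum and posting everything is a fair trade-off between openness to outside readers and release of early feasibility findings, and the sponsor may widen it voluntarily for future sub-studies. The report-timing and endpoint remarks are, respectively, loose wording already resolved by Section 4.1 and detail the plan assigns to the sub-study documentation.

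The size of the gap is unknown; the 60% of sites and 3-of-6 versions figures do not measure it. The conclusion assumes that a report is in fact delivered for every sub-study, as Section 4.1 promises, and that the unseen research agreement, sub-study plans and regulations do not restrict posting below what Section 20 states.

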## **21 STATEMENTS OF COMPLIANCE**

This clinical investigation shall be conducted in accordance with ethical principles that have their origin in the Declaration of Helsinki, International Standard ISO 14155 Clinical investigation of medical

devices for human subjects - Good Clinical Practice, and any regional or national regulations, as applicable.

## 22 QUALITY CONTROL AND ASSURANCE

In accordance with Cochlear's Quality Management System, all clinical investigations shall be conducted according to internationally recognised ethical principles for the purposes of obtaining clinical safety and performance data about medical devices.

The Sponsor employees (or designee) shall use standard operating procedures (SOP) to ensure that clinical study procedures and documentation are consistently conducted and compliant with the ISO 14155 Standard, Good Clinical Practice (GCP), and applicable local regulations.

